## 2. Attempted procedure

An attempted procedure is one where:

- The patient has been randomized to ORIGIN arm but won't receive the prosthesis (neither the VANGUARD) because the 3D preoperative planning of the design has shown shape incompatibilities or abnormalities.
- The study subject has entered the procedure room for implantation but did not receive an ORIGIN implant for any reason. (Implants broken or defective, use of another implant VANGUARD excluded in that case)

If a procedure was attempted, and the ORIGIN is not implanted, the subject will be followed for safety reporting for 30 days post-attempted implant, and then exited from the study. Adverse Events data should be collected on the AE e-CRF.

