## I. The point of enrolment

Potential subjects are identified by the Investigator or study staff based on patients' clinical and radiographic assessments during regular medical care.

The point of enrolment could be during the preoperative visit, or even earlier. The enrolment is effective and complete upon patient's signature on the approved informed consent form and after the patient has been informed of participating in the study. The Investigator or study staff provides study information and the approved Informed Consent Form (ICF) to potential subjects and answers any questions during the preoperative clinic visit. In order to provide adequate time for consideration, potential subjects will take study information and ICF home with them. When an informed decision has been made (minimum consideration time 24 hours) ICFs are returned either in person or via facsimile. Any ICFs transferred via facsimile must be returned in their original version prior to surgery. A copy of the ICF will be handed over to the patient, the signed original version will be kept and traced in the patient file.

Once the patient signs the consent form, he/she is considered as enrolled in the study and will be randomized into one of the two treatment groups: ARM 1: ORIGIN PS system or ARM 2: VANGUARD PS System right after eligibility assessment about 6 to 8 weeks prior to surgery. The randomization will automatically generate a unique subject identification code which will be used through the study participation. The institution site shall keep a log of recruited subjects based on inclusion or exclusion criteria (full name, trial number, and hospital or practice identification number), in the subject identification Log.

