### e) *Statistical Methods and Analysis*

All analyses will be described in a Statistical Analysis Plan (SAP) which will be completed prior to analysis. No interim analysis is planned.

Any deviations from this section and/or the Statistical Analysis Plan will be described and justified in the Final Clinical Study Report, as appropriate.

No statistical techniques will be used to impute missing data for continuous or categorical outcomes. If a subject's data are missing for any reason, that subject will not be included in that portion of the analysis. The number of subjects included in each analysis will be reported so that the reader can assess the potential impact of missing data.

Additional (annual) reports providing only descriptive statistics will only be written upon request of the EC/IRB and/or Regulatory Authority, as applicable.

For statistical analysis, patient satisfaction results will be analyzed into the knee awareness as:

- Never
- Almost never
- Seldom
- Sometimes
- Mostly

The subjects that required further procedures or surgeries on their knee in the initial six months were excluded from this analysis. These patients were excluded from analysis because the outcome and satisfaction scores were likely to be highly influenced by the early additional procedure, and the study was not powered to evaluate the revision rates associated with two implants.

Statistical differences could be identified in:

- Baseline demographics between ORIGIN vs VANGUARD in patient satisfaction, including slightly differences in age, comorbidities and sex.
- Surgeon overall satisfaction regarding both implants ORIGIN and VANGUARD and possible surgical factors who could play a role in the patient outcome or on the performance of the implant?
- Demonstrate superiority of ORIGIN over VANGUARD: higher score by 13.4 points based on MCID evaluation of PROMs.
- If a modular stem is used it could impact radiological analysis: radiolucencies for instance and tibial loosening

SYMBIOS		 symbios  Clinical Investigation Plan	F029.03
Date	27.11.2019		Distribution Informatique pdf
Auteur	BGA		
Contrôle	EBO		
Libération	RAQ		

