### c) *Data management*

A validated database mentioned above will be in place to store the clinical data information.

SYMBIOS		 symbios  Clinical Investigation Plan	F029.03
Date	27.11.2019		Distribution Informatique pdf
Auteur	BGA		
Contrôle	EBO		
Libération	RAQ		

Once created, it will require a validation of the protocol specific implementation of the EDC. This will be done by Symbios in collaboration with Bepatient prior to the study start.

The Data Management process regarding the data in the eCRF will include all activities related to data handling regarding:

- Data entry & processing (the data will be entered by the appropriate site personnel, listed on the Delegation Task List)
- Data security (the access to the database is secure and based on log in & password details, not accessible to an unauthorized person or individual)
- Data Validation (will ensure the most accurate validated set of data is provided for statistical analysis)
- Data controlling (via a monitor who will verify the accuracy of data entry. Completeness will be checked by authorized personnel at Symbios so that there are no unexplainable empty fields in the eCRF. This is done in order to prevent that data being overlooked by personnel entering the data).
- Database lock (quality control will be performed by the designed Data Manager in order to verify completeness). If the data is validated and no more outstanding queries or discrepancies, the data can be considered as cleaned. At this stage, the database will be locked.

In addition to the above, obvious writing and spelling errors in the eCRF may be corrected without issuing a query.

All comments have to be written in English. Any translation in the CRF should be signed and dated by the investigator.

After receipt of an Adverse Event (AE), the following must be checked immediately:

- Serious Y/N;
- Relationship to procedure/investigational product.

All decisions on the evaluability of the data from each individual subject for the statistical analysis must be made and documented before locking the database. Data will be retained for at least 15 years after investigation closure.

SYMBIOS		 symbios  Clinical Investigation Plan	F029.03
Date	27.11.2019		Distribution Informatique pdf
Auteur	BGA		
Contrôle	EBO		
Libération	RAQ		

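### ORIGIN-randomised patients whose 3D planning fails are exited before the 1-year FJS, VANGUARD has no matching rule, and no all-randomised FJS set is defined

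*Combined protocol and SAP*

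**What the plan says.** Section VII.I places randomisation "right after eligibility assessment about 6 to 8 weeks prior to surgery". Sections VII.D and VIII.F.a give the planning CT only to patients allocated to ORIGIN.

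The Attempted procedure section (VIII.F.b, item 2) names two situations. In the first, an ORIGIN-randomised patient will not "receive the prosthesis (neither the VANGUARD) because the 3D preoperative planning of the design has shown shape incompatibilities or abnormalities". In the second, the patient reaches the procedure room but does not receive ORIGIN for whatever reason, with a parenthesis that reads in part "use of another implant VANGUARD excluded in that case". In both, "the subject will be followed for safety reporting for 30 days post-attempted implant, and then exited from the study". No corresponding rule exists for a VANGUARD-randomised patient who does not receive VANGUARD. Section VII.H.a rules out replacement.

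Section X.e does not impute: if data are missing for a subject, "that subject will not be included in that portion of the analysis". It also says: "The subjects that required further procedures or surgeries on their knee in the initial six months were excluded from this analysis". The reason given is that an early further procedure would strongly influence the scores.

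On who is analysed, VII.H.c includes early discontinuations only where appropriate. X.c speaks of all enrolled patients, but under clinical data and safety outcomes. Section X.e defers detail: "All analyses will be described in a Statistical Analysis Plan (SAP) which will be completed prior to analysis". Section XI.c adds that evaluability decisions "must be made and documented before locking the database". No section defines an all-randomised set for the FJS.

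**The concern.** Planning failure is discovered after allocation, by an examination that only one arm undergoes. An ORIGIN patient with an incompatible shape leaves the study; a VANGUARD patient with the same shape is never identified, is operated on and contributes an FJS. Randomisation balanced such patients between the arms, and the exit rule undoes that balance on one side.

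The Introduction aims at Level I evidence, and that rests on comparing the groups as randomised. Section VIII.H itself lists patient-selection differences wrongly credited to the new device as a threat to interpretation.

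The six-month rule is a second post-randomisation exclusion, this time on an event that may be a consequence of the implant. It is worded for both arms. It is in the past tense and follows the knee-awareness categories, so it is unclear whether it reaches the primary FJS comparison, the satisfaction questionnaire or all patient-reported outcomes.

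**Working it through.** **Plan's own figure.** Inputs from X.a and X.b: difference 13.4, SD 26.8, two-sided alpha 0.05, power 80%.

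- n = 2/0.5² × (1.96 + 0.84)² = 62.72, so 63 per group.
- Adding 10% loss: 63/0.9 = 70 per group.

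Both figures reproduce. The issue is who is analysed, not the sample-size arithmetic. Lost numbers alone matter little: with 7 ORIGIN exits on top of the 7 planned losses (56 against 63), power by the normal approximation falls from 80.1% to 77.7%.

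**Shift in the contrast.** Let k of 70 ORIGIN patients be exited, and let D be how far their 1-year FJS would have fallen below the ORIGIN mean of those retained, m.

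- All-randomised ORIGIN mean = m − (k/70) × D.
- Mean observed after exits = m.
- Shift in favour of ORIGIN = (k/70) × D.

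The documents give neither k nor D. The values used are assumptions: k = 1, 2, 4, 7 and D = 20 to 30 points.

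**Effect on the test.** SE = 26.8 × √(2/63) = 4.775. If the all-randomised means are equal, the probability of an ORIGIN-favouring rejection is 1 − Φ(1.96 − shift/SE), which is 2.5% at zero shift.

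| Exits k | Shift, D = 20 to 30 | Share of 13.4 | ORIGIN-favouring rejection |
|---|---|---|---|
| 1 | 0.3 to 0.4 | 2 to 3% | 2.9 to 3.1% |
| 2 | 0.6 to 0.9 | 4 to 6% | 3.3 to 3.8% |
| 4 | 1.1 to 1.7 | 9 to 13% | 4.3 to 5.5% |
| 7 | 2.0 to 3.0 | 15 to 22% | 6.2 to 9.2% |

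Worked line: k = 4, D = 30 gives 4/70 × 30 = 1.71; 1.71/4.775 = 0.359; 1 − Φ(1.601) = 5.5%.

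If D = 0 there is no shift. If exited patients would have scored better, the shift would go against ORIGIN.

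**Six-month exclusion.** This cannot be sized, because the documents give no six-month re-operation rate for either arm.

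**The case against.** **The target is recipients.** Sections VI.B and VI.C word the hypothesis for patients receiving each implant, and the endpoint is timed from surgery. On that reading, planning failures lie outside the target, and the rejections tabulated above are not plainly false. The wording does matter, and it justifies an as-implanted comparison as supportive. It does not rescue the contrast: ORIGIN recipients have passed a planning screen that VANGUARD recipients never faced, so the two recipient groups are not comparable by randomisation.

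**The loss may be partly recoverable.** A reader might infer that the missing FJS is gone for good. The documents do not go that far. Section VII.H.c leaves withdrawn subjects in the centre's standard follow-up, and VIII.F.c says postoperative FJS is collected as standard of care. Some values might be retrieved, but nothing assures it. The promised SAP can define a set; it cannot supply study questionnaires that were not collected.

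**Few patients may be affected.** The exclusion criteria already remove major deformity, extreme HKA angles and excess bone loss, which makes small k more likely. For the procedure-room branch, the nearest figure is the 0.25% per-operative complication rate in IV.B, or 0.0025 × 70 = about 0.2 patients, though that counts performed procedures. It says nothing about planning failures.

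**Stronger readings that the text does not support.**

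- That every ORIGIN-randomised patient who does not receive ORIGIN is exited. The procedure-room parenthesis may place patients given VANGUARD outside the rule.
- That D should be 60.5 − 12.9 = 47.6, from the 1-year and preoperative means in IV.B. This needs every exited patient to be still unoperated at one year, and the documents do not say what surgery follows a planning failure.
- That the six-month exclusion favours ORIGIN. Its direction is unknown, it names no arm, and re-operations are still reported under X.c.

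**Conclusion.** The concern holds for planning failures: after allocation, in the ORIGIN arm only, patients are removed before the primary endpoint, and no section defines an FJS analysis that would keep them. For the procedure-room branch the rule is also one-sided, but its reach over patients given VANGUARD is unclear and the text must be reconciled.

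Under the assumed counts and deficits the shift is 0.3 to 3.0 points of 13.4, with the lower end more likely given the eligibility limits. A reader might infer that the trial is biased towards ORIGIN. The documents do not show this; it holds only if exited patients would have scored worse, which no section states.

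The six-month exclusion is a lesser point: its scope is unclear and its direction unknown.

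This should be fixed before patients are exited. Confidence is high on what the text says and low on size and direction.

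**What to change.** 1. Amend the Attempted procedure section so that ORIGIN-randomised patients who do not receive ORIGIN still complete the 1- and 2-year FJS, timed from their knee surgery or, if they have none, from a pre-specified date. The assessment schedule already has the FJS completed before surgery, so it does not require an implant.
2. Define the primary FJS analysis as all randomised patients with an available 1-year FJS, in their assigned arm. Report missing FJS by arm and reason. Allow a labelled sensitivity analysis for missing FJS, which means limiting the no-imputation sentence in X.e to the primary analysis. Report the as-implanted comparison as supportive.
3. State that the six-month re-operation exclusion does not apply to the primary FJS analysis. Keep it only as a labelled sensitivity analysis, in both arms.
4. Reconcile the VANGUARD parenthesis, and align VII.H.c, the Attempted procedure section, X.c and X.e.

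These changes concern data collection and analysis only, not which implant is used.

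**Cost.** A protocol amendment with ethics approval (XIII, XIV), SAP wording, and a few questionnaires from patients who have already consented. There is also some dilution. If k such patients score at the VANGUARD level, the expected difference is 13.4 × (1 − k/70) = 13.21, 13.02, 12.63 or 12.06 for k = 1, 2, 4 or 7. Two-sided t-test power at 63 per arm is then 78.4%, 77.2%, 74.7% or 70.7%, against 79.5% without dilution. It would be lower if any remain unoperated.

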### c) Follow-up data at 1-year visit

There is an established visit window defined in this study, the following postoperative follow-up data will be collected at 12M (1 year).

The follow-up window is flexible and is set as a guidance to +/-1M for the first visit at 1 year.

The following data will be collected in the eCRF:

- Date of visit (DD/MM/YYYY)
- Name of Surgeon
- Physical examination
  - Weight, (between 20 and 250Kg)
  - Height, (between 80 and 250cm)
  - BMI (kg/m^2)
- Radiological examination per standard of care (ap, lateral, sunrise)-
- Femoral patellar arthrosis (applicable if it is an anatomic patella not a prosthetic implant), patellar tilt angle, patellar displacement, tibial slope, femoral component flexion, anatomical axis ( $\alpha$  angle,  $\beta$  angle), mechanical axis (HKA angle, F angle, T angle, HKS angle)

SYMBIOS		 symbios  Clinical Investigation Plan	F029.03
Date	27.11.2019		Distribution Informatique pdf
Auteur	BGA		
Contrôle	EBO		
Libération	RAQ		

- Surgeon reported scores will be collected during this visit:
  - The Knee Society Score (KSS) (Objective Knee Indicators only)
  - Knee Society Radiographic Evaluation and Scoring System (KSRESS)
  - Single Leg Stance Test or (SLS)
  - Timed up and go (TUG)
- Evaluate radiographic loosening (according to the “Modern Knee Society Radiographic Evaluation System and Methodology for Total Knee Arthroplasty” version 2015)
- Radiolucent lines; Femur, frontal Tibia frontal, Tibia profil, Patella
- Satisfaction of the patient based on performance evaluation of the evaluated device ORIGIN vs VANGUARD based on scoring via FJS questionnaire:
  - FJS score
  - A self-administrated patient satisfaction questionnaire. (3 questions)

The hypothesis regarding the scoring is that patients receiving ORIGIN implants will experience a more natural feel of the prosthesis during the first year after the surgery compared to patients receiving VANGUARD implants (as measured with FJS).

The overall patient satisfaction is expected to be improved after 1-year follow-up for ORIGIN vs VANGUARD.

FJS score at the postoperative visits will be collected per standard of care at the investigational site.

- Evaluate performance of the ORIGIN System vs VANGUARD PS at 1-year follow-up: clinical examination, and scoring. To evaluate/compare the clinical, functional and quality of life outcomes with the following scores:
  - The Knee Injury and Osteoarthritis Outcome Score (KOOS)
  - The Oxford Knee Score (OKS)
  - The EQ-5D-5L Score
- Safety evaluation of the implanted device ORIGIN:
  - Evaluation of Complications using the adverse event form (Cf. Adverse events form in XXI APPENDICES)
  - Evaluation of Revisions (It is also required to complete an AE form in case of revisions)
  - Global revision rate not higher (Interval 95%:  $p > 0.05$ ) than the state of the art.

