Study endpoints:	
 
• Primary endpoint: 
 
○ To compare the ability of patients to forget their operated knee at 1 year after the surgery, measured by the Forgotten Joint Score 12 (FJS-12 Knee). The goal is to assess patient satisfaction regarding the surgery with a CE marked custom-made implant (ORIGIN®) versus off-the-shelf (VANGUARD PS) device with a self-administrated patient satisfaction questionnaire.
 
 
 
• Secondary endpoints: 
 
○ Evaluate the success of the procedure
 
○ Evaluate outcomes & complications & revision rate with the ORIGIN SYSTEM versus VANGUARD PS at the last (2y) follow-up visit
 
○ Evaluate performance of the ORIGIN System vs VANGUARD PS at 2 years follow-up: clinical examination and scoring. To evaluate/compare the clinical, functional and quality of life outcomes using the following scores: 
 
○ The Knee Injury and Osteoarthritis Outcome Score (KOOS)
 
○ The Oxford Knee Score (OKS)
 
○ The EQ-5D-5L Score
 
○ A self-administrated patient satisfaction questionnaire.
 
 
 
○ Evaluate the radiographic limb alignment, radiolucent lines and radiographic loosening (according to the “Modern Knee Society Radiographic Evaluation System and Methodology for Total Knee Arthroplasty” version 2015)
 
○ To evaluate/compare the radiological results (measurements and observations by surgeon reported scores: 
 
○ The Knee Society Score (KSS) (Objective Knee Indicators only)
 
○ Knee Society Radiographic Evaluation and Scoring System (KSRESS)
 
○ The Single Leg Stance Test (SLS)
 
○ The Timed Up & Go test (TUG)
 
 
 
 
 

N sites	1 – UMC MAINZ
Sample size	140  However, enrollment will occur at the time of the medical examination. It is assumed that the subjects’ treatments and follow-up visits will be performed per standard of care in the participating site
Total study duration:	48 months  
 
- Start- up phase: 3 months
 
- Enrolment: 18 months
 
- Follow-up phase: 24 months
 
- Study closure: 3 months
 

SYMBIOS		 symbios  Clinical Investigation Plan	F029.03

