## II. INTRODUCTION

---

ORIGIN® PS and VANGUARD® PS are total knee prostheses, intended to be used in primary Total Knee Replacement Arthroplasty (TKA) (cf. detailed products description page 12). With the ORIGIN® PS implant being customized individually made (CIM) fitting a patient's anatomy, a more natural reconstruction of knee kinematics is anticipated and ultimately a higher patient satisfaction and lower revision rate are envisioned. To date literature providing data about CIM TKA is still scarce. A study by Patil et al. assessing kinematics after TKA found that CIM TKA more closely resembled natural knee kinematics when compared to standard off-the-shelf (OTS) TKA (Patil S et al. Knee. 2015). This resemblance allows for a more natural femoral rollback during knee flexion, the authors found. Zeller et al. also came to the conclusion, that CIM TKA demonstrates knee kinematics more similar to a normal knee studying tibiofemoral kinematics using mobile fluoroscopy in vivo (Zeller IM et al. J Arthroplasty. 2017). Furthermore, CIM TKA has shown to provide a more accurate tibial fit and rotation, when compared to several standard TKA (Schroeder L et al. J Knee Surg. 2019).

A retrospective review of 621 TKA patients, 307 with CIM TKA and 314 with conventional implants, demonstrated a decreased estimated blood loss, decreased length of stay, decreased range of motion, and no discernible difference in surgical or tourniquet time (Schwarzkopf R et al. Orthop J Sports Med. 2015). Albeit, the differences found were not deemed clinically relevant, the study underlined the safety and efficacy of the CIM TKA technique. Hospital outcomes of 248 consecutive TKA patients (126 CIM TKA, 122 OTS TKA) were analyzed by Culler et al. (Culler SD et al. Arthroplast Today. 2017). Patients who received CIM TKA had lower transfusion rates and fewer adverse events.

Four year data from the UK National Joint Registry showed a cumulative percent revision rate of 0.5% for CIM TKA versus a cumulative percent revision rate of 1.9% for all TKA (National Joint Registry for England, Wales, Northern Ireland and the Isle of Man; 15th Annual Report 2018).

While all this data is encouraging, randomized controlled studies and assessments of patient reported outcomes are missing. Therefore, the current study aims to close this knowledge gap and provide Level I evidence for CIM TKA by comparing the two TKA Prostheses mentioned above and to evaluate their clinical performance and safety.

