#### b) *Safety claim*

The safety claim for the ORIGIN System is validated by the clinical evaluation. The revision rate is consistent with the state of the art. With a confidence interval of 95%, the revision rate is not higher than 2% at 1 year.

Specific claims for clinical performance and effectiveness of the ORIGIN System, is based on the state-of-the-art and is described in the clinical evaluation for the evaluated product.

The basis for the selection of the study endpoints includes the following considerations:

- They are clinically relevant and address important safety and efficacy aspects of the ORIGIN System.
- They are objectively defined and measurable in most subjects.
- They are consistent with current recommendations for endpoints in TKA clinical studies.

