### B. Clinical endpoints

#### a) *Primary endpoints*

- The hypothesis regarding the scoring is that patients receiving ORIGIN implants will experience a more natural feel of the prosthesis during the first year after the surgery compared to patients receiving VANGUARD implants (as measured with FJS)
- The primary endpoint of this study is:

SYMBIOS		 symbios  Clinical Investigation Plan	F029.03
Date	27.11.2019		Distribution Informatique pdf
Auteur	BGA		
Contrôle	EBO		
Libération	RAQ		

- To compare the ability of patients to forget their operated knee at 1 year after the surgery, measured by the Forgotten Joint Score 12 (FJS-12 Knee).
- To compare patient satisfaction regarding the surgery with a CE marked custom-made implant (ORIGIN®) versus off-the-shelf (VANGUARD PS) device. A short self-reported questionnaire will be used.

*b) Secondary endpoints will evaluate clinical performance and safety of ORIGIN System:*

- **Secondary endpoints:**

- Evaluate the success of the procedure
- Evaluate surgeon satisfaction regarding the use of implants and instruments
- Evaluate outcomes: complications & revision rate with the ORIGIN SYSTEM at the last (2y) follow-up visit
- To compare the PROMs between the two groups at 1y follow-up and 2y follow-up visits.
- Evaluate performance of the ORIGIN System vs VANGUARD PS at 2 years follow-up: clinical examination and scoring.
- To evaluate/compare the clinical, functional and quality of life outcomes using the following four scores:
  - Clinical examination
  - The Knee Injury and Osteoarthritis Outcome Score (KOOS)
  - The Oxford Knee Score (OKS)
  - The EQ-5D-5L Score
  - A self-administrated patient satisfaction questionnaire.
- To evaluate/compare the clinical, functional and quality of life outcomes with the following surgeon reported scores:
  - The Knee Society Score (KSS) (Objective Knee Indicators only)
  - Knee Society Radiographic Evaluation and Scoring System (KSRESS)
  - The Single Leg Stance Test (SLS)
  - The Timed Up & Go test (TUG)
- Radiological evaluation:
  - X-rays: AP, lateral, sunrise, long leg weight bearing film
  - Femoral patellar arthrosis: Iwano classification (stage 1 mild to 4 very severe),
  - KRESS Radiological assessment: Patellar tilt angle, patellar displacement, tibial slope, anatomical axis (angles  $\alpha - \beta$ ), mechanical axis, (HKA angle, F angle, T angle, HKS angle)

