- Safety evaluation of the implanted device ORIGIN:
  - Evaluation of Complications using the adverse event form (Cf. Adverse events form in XXI: APPENDICES)
  - Evaluation of Revisions for both Arms (It is also required to complete an AE form in case of revisions)
  - Global revision rate not higher (Interval 95%:  $p > 0.05$ ) than the state of the art.

SYMBIOS		 symbios  Clinical Investigation Plan	F029.03
Date	27.11.2019		Distribution Informatique pdf
Auteur	BGA		
Contrôle	EBO		
Libération	RAQ		

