#### *c) Analysis of clinical data and Safety outcomes*

The rate of serious adverse events (SAE) and Unanticipated Adverse Device Effects (UADEs) during the study will be presented using the proportions of patients experiencing one or more of each SAE and UADE. All serious and non-serious adverse events will be characterized in terms of severity and relatedness to the operative procedure and device. Additionally, the percent of patients requiring one or more secondary surgical procedures relating to the original procedure will be presented. Data will be analyzed for all patients enrolled in this observational study.

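### The 1- and 2-year revision criterion treats p > 0.05 as showing that ORIGIN is no worse than an unnamed benchmark, which an arm of 70 cannot show

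*Combined protocol and SAP*

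**What the plan says.** Sections VIII.F.c (1 year) and VIII.F.d (2 years) carry the same line under the safety evaluation of ORIGIN: "Global revision rate not higher (Interval 95%: $p > 0.05$ ) than the state of the art". The line gives no benchmark rate, source, test, sidedness or margin.

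Three figures elsewhere could serve as the benchmark, but none is tied to the line:

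- Section VI.A.b: "With a confidence interval of 95%, the revision rate is not higher than 2% at 1 year". This is a claim about ORIGIN attributed to the clinical evaluation, not a criterion set for this trial.
- Section II, four-year registry data: "cumulative percent revision rate of 0.5% for CIM TKA versus a cumulative percent revision rate of 1.9% for all TKA". This supplies two figures.

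None of the three is a 2-year figure.

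The arms covered also vary. The Synopsis has "revision rate with the ORIGIN SYSTEM versus VANGUARD PS at the last (2y) follow-up visit", and section VIII.F.d has "Evaluation of Revisions for both Arms", although under a heading that names ORIGIN only. The secondary endpoints in section VI.B have "complications & revision rate with the ORIGIN SYSTEM at the last (2y) follow-up visit", and section VIII.F.c names ORIGIN only.

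Section X contains no revision test. Section X.c plans descriptive percentages and says "Data will be analyzed for all patients enrolled in this observational study". Section X.e says "the study was not powered to evaluate the revision rates associated with two implants".

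**The concern.** The rule reverses the burden of proof. A small sample makes p > 0.05 easy to obtain, so the fewer patients are followed, the easier the criterion is to meet. The arm was sized for the Forgotten Joint Score (FJS) only, and the plan itself says that it lacks power for revision rates.

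Because the benchmark and test are open, whether the criterion is met also depends on choices that could be made after the data are seen.

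Section IV.D says the results will support the update of the clinical evaluation report. This trial is not the only evidence there, since section IV.B reports 399 procedures from another ORIGIN study. What is at stake is one unsupported safety statement. The primary FJS analysis is not affected.

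**Working it through.** **Inputs.** ORIGIN arm n = 70 (section VII.C). Planned loss of 7 per group, leaving 63 (section X.a). α = 0.05 (section X.a). Benchmark p₀ = 2% at 1 year is an **assumption** borrowed from section VI.A.b. The 1.9% and 0.5% of section II are used as alternatives.

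**The plan's own sample size.** n = (2/ES²)(1.96 + 0.84)² with ES = 13.4/26.8 = 0.5 gives 8 × 7.84 = 62.7, so 63 per group, and 70 with the loss allowance. This reproduces. It concerns the FJS; there is no calculation for revision.

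**How many revisions still pass, p₀ = 2%, n = 70.** Exact test: p = P(X ≥ x), X ~ Bin(70, 0.02). Score test: z = (x/70 − 0.02)/√(0.02 × 0.98/70).

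| Revisions | Observed | Exact p | Score z |
|---|---|---|---|
| 3 | 4.3% | 0.165 (pass) | 1.37 (pass) |
| 4 | 5.7% | 0.0519 (pass) | 2.22 (fail) |
| 5 | 7.1% | 0.0132 (fail) | 3.07 (fail) |

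The largest passing count is 3 (score) or 4 (exact).

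With n = 63, the exact test at 4 revisions gives p = 0.0375 and fails. The two-sided Clopper-Pearson lower limit is 1.76%, below 2%, so an interval reading still passes. The largest passing count is again 3 or 4.

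**Probability of passing, P(X ≤ 3) to P(X ≤ 4).**

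| True rate | n = 70 | n = 63 |
|---|---|---|
| 4% | 69% to 85% | 76% to 89% |
| 5% | 53% to 73% | 61% to 79% |
| 6% | 39% to 59% | 47% to 67% |

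**Other benchmarks, n = 70.**

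- At 1.9%, the largest passing count is 3 (exact, p = 0.0445 at 4; score) or 4 (Clopper-Pearson).
- At 0.5%, it is 1 (exact, p = 0.0483 at 2; score) or 2 (Clopper-Pearson).

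The undefined rule therefore tolerates anything from 1 to 4 revisions in 70, or 1.4% to 5.7%.

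**What the arm could show at best.** With zero revisions the upper limit is 1 − 0.05^(1/n) one-sided or 1 − 0.025^(1/n) two-sided:

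- n = 70: 4.2% or 5.1%.
- n = 63: 4.6% or 5.7%.

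To bring the limit to 2% with no revisions at all takes ln(0.05)/ln(0.98) = 148.3, so 149 patients, or ln(0.025)/ln(0.98) = 182.6, so 183.

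**Between-arm comparison.** For 1/70 in each arm, the Wilson limits are 0.25% and 7.66% around 1.43%. The Newcombe half-width is √[(1.43 − 0.25)² + (7.66 − 1.43)²] = 6.3 points. With 0/70 in each arm it is 5.2 points.

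**The case against.** **The line may not be a decision rule.** It is the last bullet in a list of data to be collected at each visit. It is absent from the hypothesis and from section X, where the revision analysis is descriptive. This is fair as to weight. But the line does state a condition for a conclusion, and it conflicts with the descriptive plan in X.c and the admission about power in X.e.

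**The separate SAP and the clinical evaluation may name the test and benchmark.** Neither was available, so they may fill those gaps. They cannot make p > 0.05 evidence of no excess, nor add patients.

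**Other readings are possible.**

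- If the reference to a 95% interval means that the upper confidence limit must lie below the benchmark, 70 patients cannot meet 2% even with no revisions.
- If the global rate means both arms pooled, the exact test at 2% passes up to 6 of 140 (p = 0.063), and a true 4% passes 67% of the time. A confidence-limit rule would still fail at 0/140, with an upper limit of 2.1% one-sided or 2.6% two-sided.

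The size changes with the reading; the error does not.

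**The ranges mix methods and time points.** This stands. The 89% and 79% at n = 63 rest on the Clopper-Pearson limit, the 85% at n = 70 rests on p = 0.0519, and the low end of 1 revision rests on a four-year figure for custom-made implants. With 2% or 1.9% as benchmark the range is 3 to 4. Section VII.A expects the 10% loss by the end of the study, so n = 70 suits the 1-year visit better.

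**Deleting the line leaves the denominator open.** This also stands and is taken up in the fix.

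**Conclusion.** The criterion is wrong as written, at both visits and for any benchmark: non-significance does not show that a rate is not higher. Assuming 2% at 1 year and 70 patients, it would pass a true rate of 4% with probability 69% to 85% and a true rate of 5% with probability 53% to 73%. No result in this arm, including zero revisions, could show a rate no higher than 2%.

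The pass probabilities depend on the assumed benchmark and on reading the rule as a one-sample test in the ORIGIN arm. They apply to 1 year only, because the documents give no 2-year benchmark. The point should be corrected, but it is of modest weight: revision is a secondary outcome, and the consequence is one unsupported safety statement.

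**What to change.** Delete the p > 0.05 line in sections VIII.F.c and VIII.F.d and replace it with:

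> Revision and complication rates at 1 and 2 years are reported for both arms with exact (Clopper-Pearson) 95% confidence intervals, and the between-arm difference with a 95% confidence interval (Newcombe). These results are descriptive. This study alone will not be used to conclude that the revision rate is no higher than the state of the art.

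The between-arm difference has to stay descriptive too, given an interval of about ±6.3 points with one revision per arm.

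Align section VI.B, section VIII.F.c and the ORIGIN-only safety heading at both visits with the two-arm wording of the Synopsis and section VIII.F.d.

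State the denominator for these rates. Section X.c refers to all enrolled patients, section VIII.F.b has non-implanted ORIGIN patients leave the study after 30 days, and section X.e excludes patients with further knee procedures in the first six months from the satisfaction analysis. The text should say that this exclusion does not apply to revision rates, and how early exits and incomplete follow-up are counted.

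The cost is a wording amendment, which needs ethics committee approval (section XIII). No new data are needed: the schedule of assessment (XXI.B) lists complications and revisions without limiting them to one arm. The sponsor gives up a safety statement that this trial cannot support.
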